5.7.1.6.2. Interval response modeling

To explore the interval duration effect of the double vaccination regimen, data from D28 post 2nd Vaccination of the groups 3, 7 and 9 will be analyzed using a regression model with log10 transformed VNA and ELISA results as dependent variable and interval duration as exploratory variable. Depending on the pattern observed a linear or non-linear model will be used.

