2.1. Study Rationale

Detailed information about the rationale for the selected doses can be found in Section 4.3 Justification for Dose.

Adults

In this study, safety and immunogenicity responses following 2-dose $(5x10^{10} \text{ vp}, 2.5x10^{10} \text{ vp}, 1.25x10^{10} \text{ vp})$ and single-dose $(5x10^{10} \text{ vp}, 1x10^{11} \text{ vp})$ primary vaccination regimens will be assessed in adults aged 18 to 55 years inclusive, and adults in good or stable health aged 65 years and older, to investigate dose sparing measures resulting in an increase of the number of vaccine doses available in a pandemic context. Safety and immunogenicity of 28-, 56-, and 84-day vaccination intervals for the 2-dose regimen $(5x10^{10} \text{ vp})$ will also be assessed to gather insight on the possible compression and delay of the vaccination schedule, as this may be of interest in an emergency use setting.

The $5x10^{10}$ vp dose level is administered in the Phase 3 efficacy studies VAC31518COV3001 (1-dose regimen) and VAC31518COV3009 (2-dose regimen).

In addition, an assessment of the immunogenicity of the 1.25×10^{10} vp Ad26.COV2.S dose level that is representative of the vaccine titer at the end of the foreseen shelf-life for the 5×10^{10} vp dose level in the context of emergency use with storage at 2-8 °C will be done. By lowering the dose level (ie, to 2.5×10^{10} vp and 1.25×10^{10} vp), there will also be a potential to immunobridge to a lower dose level regimen, should the efficacy study (VAC31518COV3001) provide evidence of an immune correlate of protection.

And finally, the anamnestic response after 7 days following a low-dose antigen presentation (1.25x10¹⁰ vp Ad26.COV2.S) as a surrogate of antigen exposure upon SARS-CoV-2 infection,

after the primary 2-dose or single-dose vaccination regimens, will be assessed in adult Groups 1-5, 7 and 9.

Adolescents

Available platform data, as well as safety data from the VAC31518COV1001 study, (see Section 2.2 and Section 2.3.1) support initiating evaluation of Ad26.COV2.S in adolescents aged 12 to 17 years, inclusive. In order to generate data in adolescents that will allow the use of a vaccine to prevent COVID-19 in this age group, the safety and immunogenicity responses following primary vaccination regimens will also be assessed in adolescents aged 12 to 17 years, inclusive.

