6. STUDY VACCINATION AND CONCOMITANT THERAPY

6.1. Study Vaccinations Administered

Ad26.COV2.S (also known as Ad26COVS1) will be supplied at a concentration of $1x10^{11}$ vp/mL and $2x10^{11}$ vp/mL as a suspension in single-use vials, with an extractable volume of 0.5 mL. Formulation buffer will be supplied as diluent as 15 mM citrate, 5% (w/w) hydroxypropyl- β -cyclodextrin, 0.4% (w/w) ethanol, 0.03% (w/w) polysorbate 80, 75 mM NaCl, pH 6.2, and placebo will be supplied as a 0.9% NaCl solution.

Adult participants in Groups 1-6 will be vaccinated on Day 1 and Day 57, in Groups 7-8 on Day 1 and Day 29, in Groups 9-10 on Day 1 and Day 85.

Adolescent participants in Groups A-B will be vaccinated with a single dose of Ad26.OV2.S at 2.5×10^{10} vp on Day 1. Adolescent participants in Group C who received placebo on Day 1 will receive a single dose of Ad26.OV2.S at 2.5×10^{10} vp following unblinding at approximately 6 months of study participation.

A volume of 0.5 mL will be administered to all (adult and adolescent) participants.

• Ad26.COV2.S:

 $1x10^{11}$ vp dose level (Adult Group 4): 0.5 mL is withdrawn from one vial containing 0.75mL $2x10^{11}$ vp/mL.

 $5x10^{10}$ vp dose level (Adult Groups 1, 5, 7, 9): 0.5 mL is withdrawn from one vial containing 0.75 mL $1x10^{11}$ vp/mL.

 2.5×10^{10} vp dose level (Adult Group 2, and Adolescent Groups A, B and C): 0.75 mL of formulation buffer is added to a vial containing 0.75 mL 1×10^{11} vp/mL, providing 5×10^{10} vp/mL in a vial with an extractable volume of more than 1 mL. Then 0.5 mL will be withdrawn from this vial.

 1.25×10^{10} vp dose level (Adult Group 3 and antigen presentation in Groups 1-5, 7 and 9): 0.4 mL is withdrawn from one vial containing 0.75 mL 1×10^{11} vp/mL and added to a vial containing 1.2 mL formulation buffer, providing 2.5×10^{10} vp/mL in a vial with an extractable volume of more than 1 mL. Then 0.5 mL will be withdrawn from this vial.

• Placebo: 0.9% NaCl solution (Groups 6, 8, and 10): 0.5 mL

Study vaccine will be administered by IM injection into the deltoid muscle, preferably of the non-dominant arm. Subsequent vaccinations are preferably administered in the opposite arm. If an injection cannot be given in the deltoid muscle due to a medical or other contraindication (for

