9.2.1. Immunogenicity

The primary objective in the adult population of the study is to explore the dose-response and interval-response relationship of humoral immune responses induced by different dose levels and different vaccine administration timings of Ad26.COV2.S using VNA titers and ELISA U/mL.

To explore the dose-response relationship between VNA/ELISA and different dose levels of the Ad26.COV2.S vaccine, a separate linear regression model will be fitted for:

- all active groups 14 days post vaccination 1
- all active groups 28 days post vaccination 1
- the 2-dose active groups using data of Groups 1-3, 28 days post vaccination 2
- the single-dose active groups using data of Groups 4-5, 28 days post vaccination 2
- the 2-dose active groups, using data of groups 1-3, 14 days post vaccination 2

In the linear regression model the log transformed VNA/ELISA titers at each timepoint will be used as dependent variable and the dose levels as independent variable.

Depending on the model fit, other models (eg, log-linear models or EMAX models) may be explored as well for the 56-day interval regimen.

Details on the comparison between the different dose levels and vaccination interval groups will be outlined in the SAP.

9.2.2. **Safety**

Placebo recipients are included for blinding and safety purposes and will provide additional control specimens for the immunogenicity assays.

While mild to moderate vaccine reactions (local site and systemic responses) are expected, AEs that preclude further dose administration or more serious ones that would limit product development are not anticipated. The observation of 0 events (eg, SAEs) is associated with 95% confidence that the true event rate is below the rates specified in Table 9 for the considered number of participants.

Table 9: Upper Limit of the 95% One-sided Confidence Interval if no Cases are Observed for Different Sample Sizes

Sample Size	N=25	N=50	N=75	N=150
Upper Limit 95% one- sided CI	11.3%	5.8%	3.9%	2.0%

CI = confidence interval, N = number of participants

Table 10 provides the probability of observing at least one AE in a group of the considered sample size given several true AE rates.

True AE Rate	Probability of Observing at Least One AE in N Participants (%)				
(%)	N=25	N=50	N=75	N=150	
0.5	12	22	31	53	
1	22	39	53	78	
2.5	47	72	85	98	
10	93	99	>99.9	>99.9	
25	>99.9	>99.9	>99.9	>99.9	
50	>99.9	>99.9	>99.9	>99.9	

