5.7. Other Analyses

5.7.1. Immunogenicity Analyses

The analysis of immunogenicity will use the PPI set, PPI modified set and FAS modified set (cf Appendix 2 for analyses sets definitions). Immunogenicity analyses will also be done on the FAS (participants who became infected during the study will be analyzed as a subgroup and shown in the graphs using different colors and symbols). Data will be analyzed by vaccine group, and by vaccine group and age group^a.

Key immunogenicity assay results will also be analyzed for the subgroups defined in Section 5.7.4. Data will be presented by scheduled time point. For the PPI analysis, samples taken outside of the allowed window will be excluded from the tables and graphs (but will be included in the listings and clearly marked as results not included in the PPI analyses). For the FAS analysis, samples taken outside of the allowed window will be included.

Note: analyses that are potentially unblinding at the individual participant level (e.g. graphs showing individual data tied to COVID-19 infection status, especially when the number of COVID-19 infections is low and/or when time of infection is indicated) will be carried out after official unblinding of the trial, or will be carried out exclusively on specific groups (or other clearly defined subgroups) after these are unblinded. Alternatively, prior to unblinding, these analyses can be performed in a completely blinded manner (e.g. tables with only a single column pooling all regimens).

^a As indicated previously, all analyses, including the immunogenicity analyses, will be conducted by actually received vaccine (“as treated” principle). Note that the statistical tables are designed with the planned vaccine regimens as columns. Therefore, participants who receive e.g. “Placebo, Placebo” instead of “Ad26.COV2.S 5x10¹⁰ vp, Placebo” will appear in the “Placebo, Placebo” column. However, to avoid sparse columns, participants who receive e.g. “Placebo, Ad26.COV2.S 5x10¹⁰ vp” (which is not a planned vaccine regimen) will be excluded from the statistical tables. They will be included in the listings, as well as in the programmed patient narratives where they will appear as “Subjects with vaccine misallocation”.

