5.7.1.6. Statistical modeling of the immune responses

The VNA and ELISA results at D14 and D28 post 1st Vaccination and post 2nd Vaccination will be used to investigate potential dose-response effects. For the D28 post 2nd Vaccination also a potential interval duration effect between the two vaccinations will be explored.

In all modeling approaches the VNA and ELISA data will be log10 transformed.

All modeling exercises are explorative in nature and not powered for formal hypothesis testing.

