6.2. Appendix 2 Changes to Protocol-Planned Analyses

In October 2020, the current study was temporarily paused because one of the pausing rules was met in study COV3001. When the pause was lifted, most of the participants in Groups 7-8 had missed their visit window for Vaccination 2, rendering the intent of the 28-day vaccination interval in these groups futile.

For safety analyses,

- the 2 subjects vaccinated before pausing rule (28-day interval) will only be shown in the listings.
- the other subjects received the vaccination 2 between 51 and 72 days after Vaccination 1. They will be integrated in the Full Analysis Set with groups 1 and 6 (56-day interval).

For immunogenicity analyses,

- subjects randomized in groups 7 and 8 won't be included in PPI set
- a modified PPI set will be defined as follows :
subjects with vaccination 2 within the window (54-64) or subjects who did not receive vaccination 2 will be integrated in groups 1 and 6
- a modified FAS set will be defined as follows :
subjects in mPPI set and subjects with vaccination 2 in (51-53) days or (65-72) days window

6.3. Appendix 3 Guidance for Industry: Toxicity Grading Scale for Healthy Adult and Adolescent Volunteers Enrolled in Preventive Vaccine Clinical Trials

The laboratory values provided in the tables below serve as guidelines and are dependent upon institutional normal parameters. Institutional normal reference ranges should be provided to demonstrate that they are appropriate.

If a laboratory value falls within the grading as specified below but also within the local laboratory normal limits, the value is considered as normal.

Serum *	Mild (Grade 1)	Moderate (Grade 2)	Severe (Grade 3)	Potentially Life Threatening (Grade 4)**
Sodium – Hyponatremia mEq/L	132 – 134	130 – 131	125 – 129	< 125
Sodium – Hypernatremia mEq/L	144 – 145	146 – 147	148 – 150	> 150
Potassium – Hyperkalemia mEq/L	5.1 – 5.2	5.3 – 5.4	5.5 – 5.6	> 5.6
Potassium – Hypokalemia mEq/L	3.5 – 3.6	3.3 – 3.4	3.1 – 3.2	< 3.1
Glucose – Hypoglycemia mg/dL	65 – 69	55 – 64	45 – 54	< 45
Glucose – Hyperglycemia Fasting – mg/dL Random – mg/dL	100 – 110 110 – 125	111 – 125 126 – 200	>125 >200	Insulin requirements or hyperosmolar coma
Blood Urea Nitrogen BUN mg/dL	23-26	27 – 31	> 31	Requires dialysis
Creatinine – mg/dL	1.5 – 1.7	1.8 – 2.0	2.1 – 2.5	> 2.5 or requires dialysis
Calcium – hypocalcemia mg/dL	8.0 – 8.4	7.5 – 7.9	7.0 – 7.4	< 7.0
Calcium – hypercalcemia mg/dL	10.5 – 11.0	11.1 – 11.5	11.6 – 12.0	> 12.0

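### The interval-response model uses Group 3 (1.25×10^10 vp) as its 56-day arm where the 5×10^10 vp arm, Group 1, is needed, so dose is confounded with interval

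*SAP*

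**What the plan says.** SAP Section 5.7.1.6.2 specifies one interval-response analysis: "data from D28 post 2nd Vaccination of the groups 3, 7 and 9 will be analyzed using a regression model". The outcome is log10 VNA or ELISA, interval duration is the only regressor, and the choice between a linear and a non-linear form is left to the data.

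The protocol frames the question within one dose. Section 2.1 proposes to assess "Safety and immunogenicity of 28-, 56-, and 84-day vaccination intervals for the 2-dose regimen" at 5×10^10 vp. Section 6.1 lists the 5×10^10 vp groups as "dose level (Adult Groups 1, 5, 7, 9): 0.5 mL is withdrawn from one vial containing" and the 1.25×10^10 vp use as "dose level (Adult Group 3 and antigen presentation in Groups 1-5, 7 and 9". Table 2 of Section 4.1 agrees: Groups 1 and 3 share the 56-day interval but have different doses.

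Interval-response is part of the main adult aim. Protocol Section 9.2.1 says "The primary objective in the adult population of the study is to explore the dose-response and interval-response relationship of humoral immune responses", and SAP Section 5.3.1 repeats the aim. SAP Section 5.7.1.6 adds the caveat "All modeling exercises are explorative in nature and not powered for formal hypothesis testing".

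On analysis sets, SAP Section 5.7.1 says "The analysis of immunogenicity will use the PPI set, PPI modified set and FAS modified set", and the FAS is used as well. Because of the study pause, SAP Appendix 2 says "subjects randomized in groups 7 and 8 won't be included in PPI set". For the modified PPI set it moves those given vaccination 2 in the 54–64 window into Groups 1 and 6.

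**The concern.** The 56-day arm in the model differs from the other two arms in dose as well as interval, by a factor of 5×10^10 / 1.25×10^10 = 4, and there is no dose term. The dose-response models in SAP Section 5.7.1.6.1 allow titres at this same time point to depend on dose across Groups 1–3. The interval model in effect assumes that they do not.

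The protocol wants the interval results to inform compressing or delaying the schedule. If titres rise with dose, this model would make a longer interval look better even where interval has no effect.

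**Working it through.** The documents give no expected result, sample size or power for this model, so there is no figure to reproduce. The check is the expected least-squares slope when interval truly has no effect.

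**Inputs from the documents**
- Group 3: n = 75, 56 days, 1.25×10^10 vp.
- Group 7: n = 50, planned at 28 days, 5×10^10 vp.
- Group 9: n = 50, 84 days, 5×10^10 vp (Protocol Section 4.1 and Table 2).
- Group 7 after the pause: one participant at 28 days (footnote in Protocol Section 4.1), the others at 51–72 days (SAP Appendix 2). Assuming full enrolment and vaccination, that leaves 49.

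**Assumption not in the documents:** expected log10 titre at 1.25×10^10 vp is lower than at 5×10^10 vp by d = 0.1, 0.2 or 0.3. If d = 0, every bias below vanishes.

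**Formula.** Set the expected log10 titre to −d in Group 3 and 0 elsewhere. With x̄ the weighted mean interval and Sxx = Σn(x − x̄)², the slope is

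b = 75·d·(x̄ − 56) / Sxx

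and the apparent fold change per 28 days is 10^(28b).

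**Planned design (28/56/84 days).** x̄ = (75×56 + 50×28 + 50×84)/175 = 56, so b = 0 and the linear slope is unbiased. A quadratic has three parameters for three intervals, so it passes through 0, −d, 0. It shows a false dip at 56 days to 10^(−d) = 0.79 / 0.63 / 0.50 of the level at 28 and 84 days.

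**PPI set (Group 7 excluded).** x̄ = (75×56 + 50×84)/125 = 67.2. Sxx = 75×11.2² + 50×16.8² = 23,520. b = 75d×11.2/23,520 = d/28. The false fold change is 10^d = 1.26 / 1.58 / 2.00.

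**Modified sets.** In the modified PPI set the usable Group 7 participants sit in Group 1, which the model does not use, so the result is the same. The modified FAS is built on the modified PPI set. Appendix 2 does not say which group the extra participants (51–53 and 65–72 days) join, so the same result there is an inference.

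**Unmodified FAS.** Appendix 2 does not reassign Group 7 here for immunogenicity. If it stays in at its actual intervals:

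| Group 7 placement | x̄ | Sxx | 28b per unit d | Fold at d = 0.1 / 0.2 / 0.3 |
|---|---|---|---|---|
| 49 at 56 days, 1 at 28 | 63.84 | 29,228 | 0.563 | 1.14 / 1.30 / 1.48 |
| 49 evenly over 51–72, 1 at 28 | 65.38 | 28,041 | 0.703 | 1.18 / 1.38 / 1.63 |
| 49 evenly over 51–72 | 65.60 | 26,636 | 0.757 | 1.19 / 1.42 / 1.69 |
| 49 at 51 | 62.64 | 32,758 | 0.426 | 1.10 / 1.22 / 1.34 |
| 49 at 72 | 68.55 | 24,331 | 1.083 | 1.28 / 1.65 / 2.11 |

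The last two rows are extremes and omit the 28-day participant. Including that person gives 1.10 / 1.20 / 1.32 and 1.26 / 1.58 / 1.99.

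**With Group 1 in place of Group 3**, every arm is at 5×10^10 vp, d drops out, and the dose bias is zero in each case.

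**The case against.** The strongest reply is that little depends on this model. It is declared exploratory, there is no formal testing, and the primary endpoints are per-group responses and geometric means. SAP Section 5.7.1.5.1 also plans geometric mean ratios against the 5×10^10 vp vaccine and plots that combine regimens, so a reader could compare Groups 1 and 9 directly. All of that is true, and it limits the consequence. It does not make the specified model answer its own question.

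The choice of Group 3 is probably a drafting slip. Appendix 2 treats Group 1 as the match for the delayed Group 7 participants, so the SAP's own logic points to Group 1. That supports the correction.

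Complete confounding also depends on using nominal intervals, and the SAP does not say whether nominal or actual intervals are meant. Vaccination 2 has a −3/+7 day window in Groups 3 and 9 (Protocol Tables 4 and 6). With intervals spread evenly over a 10-day window, Sxx rises by 125×100/12 to about 24,562, and 1.26 / 1.58 / 2.00 becomes 1.25 / 1.55 / 1.94. Confounding is then nearly complete, and the conclusion is the same.

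Finally, the dose effect is assumed. Protocol Section 4.3 cites potent responses to other Ad26 vaccines at or below 1.25×10^10 vp, so a negligible difference cannot be ruled out. The plan cannot rely on that, because it sets out to estimate this very dose effect.

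**Conclusion.** The concern holds. As written, the model combines two doses four-fold apart with no dose term, and nothing in either document supports the choice of Group 3. In the PPI set, and in the modified sets on the reading above, a dose effect of 0.1 to 0.3 log10 would appear as a 1.26- to 2.00-fold benefit of moving from 56 to 84 days. In the unmodified FAS, if Group 7 is kept, the false effect is smaller for most placements (1.14- to 1.69-fold across the three central ones). Only under the planned 28/56/84 schedule is the linear slope unbiased, and that schedule did not survive the pause.

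These figures rest on the assumed dose effect, planned group sizes and no true interval effect. They are expected values, so they need no standard deviation. The primary per-group estimates are unaffected. The correction should be made because this is the only interval-response model for a stated part of the adult primary immunogenicity objective.

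**What to change.** In SAP Section 5.7.1.6.2, replace the group list with the two-dose 5×10^10 vp groups: Group 1, including the Group 7 participants merged into it under Appendix 2, and Group 9. In the same place:

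- Name the analysis set or sets.
- Say that participants without vaccination 2, whom Appendix 2 also merges, have no interval and do not enter this model.
- State that without a 28-day arm the model covers about 51 to 84 days in the modified FAS, and from 54 days in the modified PPI set.
- Preferably use each participant's actual interval as the regressor. This is not needed to remove the dose confounding.

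Optionally, show the open-label 28-day recipients from Groups 6, 8 and 10 as a separately labelled, non-randomised comparison. That must first be reconciled with Protocol Section 9.4.2, which has adult data analysed separately from the point of unblinding.

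The group correction costs one line of SAP text, with no new data and no change to trial conduct. The optional comparison needs its own paragraph.

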5.7.2. COVID-19 case monitoring to detect imbalances across study groups (harm monitoring)

An unblinded statistician, who is not otherwise involved in the study, will monitor the number and severity of molecularly confirmed COVID-19 cases in the Ad26COVS2.S and placebo groups to identify an imbalance between groups if it occurs. The unblinded statistician will inform the DRC as soon as an imbalance between groups is detected.

As soon as 3 confirmed COVID-19 cases have occurred, and with every additional case, the unblinded statistician will tabulate the cases according to whether the participant received Ad26.COV2.S or placebo (i.e. active regimens will be pooled) and calculate the difference in proportions between the two groups (proportion in active – proportion in placebo). Two (two-sided) confidence intervals around this difference will be constructed, a 95% CI and an 80% CI (i.e. using z-values corresponding to alpha = 0.05 and alpha = 0.20), using Newcombe’s method without continuity correction.

The Newcombe’s confidence interval for a difference between proportions is calculated as follows:

$$\begin{aligned} \text{Lower limit: } & (\hat{p}_1 - \hat{p}_2) - \sqrt{(\hat{p}_1 - L_1)^2 + (U_2 - \hat{p}_2)^2} \\ \text{Upper limit: } & (\hat{p}_1 - \hat{p}_2) + \sqrt{(U_1 - \hat{p}_1)^2 + (\hat{p}_2 - L_2)^2} \end{aligned}$$

Where L_i and U_i are the Wilson Lower and Upper confidence limits for p_i . The Wilson confidence limits without continuity correction for each binomial proportion $p_i = x_i/n_i$ ($i=1,2$) is given by:

$$\frac{1}{2(n_i + z^2)} \left((2n_i \hat{p}_i + z^2) \pm z \sqrt{4n_i \hat{p}_i (1 - \hat{p}_i) + z^2} \right)$$

If the upper limit of the one-sided 95% CI around the difference in proportions exceeds 0.10 (i.e. >10 percentage points difference between active and placebo), and the lower limit of the one-sided 80% CI around the difference in proportions exceeds 0 (i.e. >0 percentage points difference between active and placebo), then the unblinded statistician will conclude that there is an imbalance between active and placebo (where the proportion in active is greater than the proportion in placebo). Otherwise, the statistician will not conclude that there is an imbalance.

The same operations will be executed for severe COVID-19 cases, using these definitions of “severe” cases:

- COVID-19 cases requiring hospitalization,
- COVID-19 cases requiring hospitalization and the patient being admitted to the Intensive Care Unit,
- COVID-19 cases resulting in death (with death being at least probably related to COVID-19)

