Vaccine-associated enhanced disease has been described for SARS-CoV and MERS-CoV in some animal models, 0,0,0,0,0 and is associated with non-neutralizing antibodies and a Th2-skewed immune response. In contrast, the Ad26-based vaccines have been shown to induce a clear Th1-skewed immune response and generate potent neutralizing antibody responses in both humans and animal models (see Section 2.2, Background). Participants in the present study will be informed of the theoretical risk of disease enhancement in the ICF. Furthermore, as a risk mitigation strategy, all participants in the study will be passively and actively monitored for acquisition of molecularly confirmed COVID-19 (see Section 4.1, Section 8.1.2, and Section 10.8). This active and passive surveillance system for detection of COVID-19 will ensure rapid identification of COVID-19 and will ensure that appropriate treatment procedures can be initiated to reduce the risk of enhanced disease if it should occur. Selected members of the statistical programming and the statistics group

will receive individual level unblinded data pertaining to study VAC31518COV2001 when unblinding at the participant level is required. They will monitor the number and severity of molecularly confirmed COVID-19 cases in the Ad26.COV2.S and placebo groups to identify an imbalance between groups if it occurs. They will immediately inform the SMC as soon as an imbalance between groups is detected. A prespecified threshold (imbalance above a certain percentage and/or number of cases) that will trigger notification of the SMC will be described in the Statistical Analysis Plan (SAP).

Unknown Risks

There may be other risks that are not known. If any significant new risks are identified, the investigators and participants will be informed.

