The Statistical Support Group (SSG) will provide individual level unblinded data pertaining to study VAC31518COV2001 when unblinding at the participant level is required (see Section 10.3.6). In addition, they will monitor the number and severity of molecularly confirmed

COVID-19 cases in the Ad26.COV2.S and placebo groups to identify an imbalance between groups if it occurs (see Statistical Analysis Plan). They will inform the SMC as soon as an imbalance between groups is detected. Participants, clinical staff, and study-site personnel will remain blinded to the study vaccine allocation until implementation of protocol Amendment 5 (adults) or Amendment 6 (adolescents). A prespecified threshold (imbalance above a certain percentage and/or number of cases) that will trigger notification of the SMC will be described in the SAP.

The SAP will describe the planned analyses in greater detail.

Participants unblinded due to administration of an authorized/licensed COVID-19 vaccine

Investigators may receive requests to unblind study participants who become eligible to receive an authorized/licensed COVID-19 vaccine if/when these become available. In these cases, the investigator will discuss with the participant available options and ramifications. If the participant is eligible for an authorized/licensed vaccine according to local immunization guidelines or recommendation and if the participant wishes to proceed with the unblinding, the investigator will follow the unblinding procedures. The reason for the unblinding request should be documented.

When unblinding, if it is determined that the participant received the Ad26.COV2.S vaccine (and not placebo), the participant will be informed that there are no data on the safety of receiving 2 different COVID-19 vaccines. Participants who were already unblinded for any reason may receive Ad26.COV2.S vaccine upon discussion with the investigator, provided that they did not receive a COVID-19 vaccine. Unblinded participants, whether in the vaccine or control group, will be asked to continue to be followed in this study in line with the Schedule of Activities to the extent that the participant is amenable. All data will be analyzed separately from the point of unblinding for safety and immunogenicity, as described in the SAP.

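### The COVID-19 harm rule in SAP 5.7.2 needs an upper 95% limit above 0.10, so at full adult enrolment it first alerts at 37 vaccine cases to 0 placebo cases (35 to 0 on two-sided limits), for deaths as for all cases

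*SAP*

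**What the plan says.** Protocol 2.3.1 offers unblinded monitoring of confirmed COVID-19 as mitigation for the theoretical risk of enhanced disease: "They will immediately inform the SMC as soon as an imbalance between groups is detected". Protocol 9.5 leaves the trigger to the SAP: "A prespecified threshold (imbalance above a certain percentage and/or number of cases) that will trigger notification of the SMC".

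SAP 5.7.2 supplies it. From the third confirmed case, and at each further case, active regimens are pooled and compared with placebo by Newcombe limits for the difference in proportions (active minus placebo). The intervals are introduced as two-sided: "Two (two-sided) confidence intervals around this difference will be constructed, a 95% CI and an 80% CI". The decision sentence then speaks of one-sided limits and requires two things together:

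- "If the upper limit of the one-sided 95% CI around the difference in proportions exceeds 0.10", explained as "i.e. >10 percentage points difference between active and placebo";
- "lower limit of the one-sided 80% CI around the difference in proportions exceeds 0".

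If either fails, no imbalance is concluded. For serious outcomes, "The same operations will be executed for severe COVID-19 cases". These are hospitalisation, ICU admission, and "COVID-19 cases resulting in death (with death being at least probably related to COVID-19"), with no separate threshold.

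**The concern.** A harm alarm should respond to evidence that an excess exists. An upper limit above 0.10 is not such evidence: it says that an excess of 10 points remains compatible with the data. It does not show a difference of more than 10 points, as the SAP's explanation implies. The limit falls towards the observed difference as the denominators grow, so a real excess of a few points meets the condition most easily when there are few data and fails it when there are many.

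Both conditions are required, so the lower-limit condition, which does respond to evidence, cannot raise an alert by itself. At stake is whether the mitigation promised in the protocol works for moderate excesses and for severe disease, and whether a statement of no imbalance from the blinded period can be taken as reassurance.

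**Working it through.** **Inputs.** Group sizes from the Protocol synopsis: active 5 × 75 + 50 + 50 = 475; placebo 3 × 25 = 75; total 550, which matches the stated adult target. One-sided limits use z = 1.645 (95%) and 0.8416 (80%); two-sided limits use 1.960 and 1.2816. The plan gives no alert count, so there is no figure of its own to reproduce.

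**Formulas (SAP 5.7.2).** Wilson limits for x/n: [(2np + z²) ± z√(4np(1−p) + z²)] / [2(n + z²)]. Newcombe upper limit: (p1 − p2) + √[(U1 − p1)² + (p2 − L2)²]. Lower limit: (p1 − p2) − √[(p1 − L1)² + (U2 − p2)²].

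**No placebo cases.** Here p2 = L2 = 0, so the Newcombe upper limit reduces to U1, the Wilson upper limit of the vaccine arm alone.

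| Vaccine : placebo cases | Limits | Upper 95% | Lower 80% | Alert |
|---|---|---|---|---|
| 36 : 0 | one-sided | 0.0983 | 0.062 | no |
| 37 : 0 | one-sided | 0.1006 | 0.064 | yes |
| 34 : 0 | two-sided | 0.0984 | 0.046 | no |
| 35 : 0 | two-sided | 0.1008 | 0.048 | yes |

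The lower limit alone passes 0 at 5:0 (one-sided, 0.0006) or 11:0 (two-sided, 0.0005). The upper-limit condition therefore causes the delay from 5 to 37, or from 11 to 35. For scale, 36:0 has a one-sided Fisher p of 0.004. With 1, 2 and 3 placebo cases the first alerts are 42, 46 and 50 vaccine cases (one-sided) or 40, 44 and 48 (two-sided).

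**Smaller denominators, no placebo cases (one-sided / two-sided).** 356 v 56: 27 / 25. 238 v 38: 17 / 15. 190 v 30: 13 / 11. 95 v 15: 5 / 10.

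**Similar excess, more data.** One-sided: 6/95 v 0/15 (6.3%) has upper 0.118 and lower 0.015 and alerts; 28/475 v 0/75 (5.9%) has 0.079 and 0.046 and does not. Two-sided: 11/190 v 0/30 (5.8%) has 0.101 and 0.003 and alerts; 28/475 v 0/75 has 0.084 and 0.034 and does not.

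**Chance of an alert at 475 v 75.** Single look: the sum of independent binomials over the alert region. Every-case look: exact, by counting case orderings that never enter that region from the third case on. The rates are assumptions, because the documents give none.

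| True rates, vaccine v placebo | One-sided, single look | One-sided, every case | Two-sided, single look |
|---|---|---|---|
| 5% v 1% | 0.3% | 0.3% | 0.8% |
| 6% v 1% | 3.4% | 3.5% | 6.7% |
| 6% v 2% | 1.7% | 1.9% | 3.5% |
| 10% v 5% | 31% | 34% | 39% |
| 10% v 2% | 70% | 72% | 78% |
| 15% v 5% | 94% | 95% | 93% |
| severe, 2% v 0.2% | 0% | 0% | 0% |

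The SAP does not say who counts in n at each look. Taking n as those vaccinated to date (assumed uniform accrual over 1 or 3 months, 6 months' follow-up, 6,000 simulated trials per scenario) hardly changes the one-sided every-case figures: 0.2–0.3% for 5% v 1%, 71% for 10% v 2%, 95% for 15% v 5%, and 0% for severe.

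**The case against.** The strongest point is timing. Amendment 5, dated 18 May 2021, unblinds all adults (Protocol 6.4), and SAP section 4 censors COVID-19 analyses at unblinding. An SAP written for Amendment 6 may have little or no blinded adult period left to monitor, and no section plans to publish a statement of no imbalance. This stands. It moves the weight from the alert itself to how a silent alarm is later read, but does not make the rule sound.

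The headline counts assume full enrolment and no placebo cases, and alerts come earlier with fewer participants. The contrasting examples are separate data sets, and a notification already sent is not withdrawn. Both remarks are fair. However, the detection figures average over placebo counts and remain near zero for excesses of 4 points, including under the growing denominators simulated.

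There are other routes to review. The medical monitor or investigator may initiate committee review for any single event (Protocol 6.10), and the committee may require unblinded data (Protocol 10.3.6). SAP 5.7.3 also tabulates confirmed infections by regimen, with a narrative for each case. None of these corrects the rule, and 5.7.3 has no per-arm counts by severe definition and no Newcombe limits.

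Finally, the protocol asks for a percentage or a number of cases, and 10 points is a percentage. That wording does not require testing it against an upper limit. How far to trade sensitivity against false alerts is partly a matter of judgement, so the z-values proposed below are adjustable.

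**Conclusion.** The rule is wrong as written, on either reading of the limits. At 475 v 75 with no placebo cases it is silent up to 36 vaccine cases (34 on two-sided limits). Because the operations are the same, 36 vaccine-arm deaths to 0 (34 on two-sided limits) would not be called an imbalance either.

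The alert counts follow from the SAP's formulas and the planned group sizes. The detection rates also rest on assumed attack rates: the rule almost never finds excesses of 4 to 5 points when the placebo rate is 1% (0.3% to 6.7% in a single look across the two readings), and it does find 15% v 5%. A finding of no imbalance from the blinded period should not be used as reassurance, least of all for severe disease. The conflict between one-sided and two-sided limits and the undefined n also need settling. This should be fixed. It is a wording change, and the passing of the blinded period limits its practical reach.

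**What to change.** Delete the upper-limit condition for all cases and for the three severe definitions. Notify the IDMC (5.7.2 still names the DRC) when the lower 80% Newcombe limit exceeds 0. State each z-value and who counts in n at each look, for example those vaccinated by that date.

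- **All cases: two-sided 80% limit (z = 1.2816).** Alerts at 11:0, 22:1 and 31:2. Detection (single look / every case): 72% / 82% for 5% v 1%; 84% / 91% for 6% v 1%; 62% / 76% for 6% v 2%; 95% / 98% for 10% v 2%.
- **Severe definitions: one-sided 80% limit (z = 0.8416).** Alerts at 5:0, 15:1 and 24:2. Detection: 83% / 89% for 2% v 0.2%; 48% / 49% for 1% v 0.1%. The two-sided limit would give 30% / 31% and 0.9% / 0.9%.

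If the blinded period has closed, report counts per arm with 80% and 95% Newcombe limits for all cases and each severe definition, in place of a yes-or-no conclusion on imbalance.

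**Cost.** More false alerts with no true difference and a look at every case. For all cases: 10.6%, 18.9%, 25.1% and 33.0% when both arms have 2%, 3%, 5% and 10%, against 0%, 0%, 0.02% and 5.5% now on one-sided limits (8.4% at 10% on two-sided). For severe definitions: 0.3%, 6.9%, 30.8% and 47.9% when both arms have 0.2%, 0.5%, 1% and 2%, against 0% now. Each alert leads only to committee review.

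The two-sided limit is not better everywhere than the current rule on one-sided limits. At 95 v 15 it first alerts at 10:0 against 5:0, and at 15% v 10% a single look detects 45% against 54% (71% against 61% with every-case looks). Using the one-sided 80% limit for all cases would never alert later than the current rule, but false alerts would be 48% to 65% when both arms have 2% to 10%.
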